### Schema

1 Cycle = 28 Days

\* Submit slides for Central Pathology BRAF IHC within 28 days after pre-registration. Once slides are received at BWH/DFCI, results will be returned within 14 days. Register patient within 21 days of result notification. See Sections [4.3](#), [4.4](#), and [6.2.1](#) for complete instructions.

\*\* Discontinue vemurafenib + cobimetinib at progression, unacceptable adverse event, or drug hold  $>28$  days. After discontinuation of vemurafenib and cobimetinib, subsequent treatment is at the discretion of the treating physician.

\*\*\* Patients on Cohort A may continue treatment with vemurafenib and cobimetinib beyond 5 cycles in special circumstances with study chair approval. See [Section 7.1.1](#) for more information.

Patients will be followed for 5 years from study registration (Step 1) or until death, whichever comes first.

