- 9 Medication diaries should be completed by the patient throughout treatment, and should be collected at day 1 of every cycle starting with day 1 cycle 2. Please use [Appendix III](#) and [IV](#).
- 10 It is suggested that the treating physician communicate with the endocrinologist to make any adjustments to the endocrine medications that the patient is on.
- A Eye exam that includes retinal exam, slit lamp exam, and visual fields (preferably Goldmann Visual Field testing if available) required prior to registration, then every 2 months (+/- 1 month) for 1 year, then every 6 months (+/- 2 months) while on protocol treatment, and within 28 days after completion of treatment (ONLY if an eye exam has NOT been performed within 28 days prior to last dose of vemurafenib.) Visual field testing reports must be submitted as supporting documentation for each timepoint specified in this footnote. See [Section 8.2.2.7](#) for dose modifications.
- B Required prior to treatment, then performed every 28 days (+/- 7 days) for 3 months, then every 3 months (+/- 1 month) while on vemurafenib. See [Section 8.2.2.6](#) for instructions regarding initiation of treatment and dose modifications.

- C Echo or MUGA should be performed prior to treatment, after 1 month (+/- 5 days) of treatment, and every 3 months (+/- 1 month) while on cobimetinib. See [Section 8.2.2.5](#) for instructions regarding initiation of treatment and dose modifications.
- D Skin exam (preferably by dermatology) to screen for malignancy required prior to treatment, then every 6 months (+/- 3 months) while on protocol treatment, then at discretion of treating physician once off protocol treatment. Skin exam should look for: rash, pruritis, dry skin, keratoacanthoma, squamous cell carcinoma, Hyperkeratosis, hand-foot syndrome.

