### 7.1 Vemurafenib + cobimetinib

Each cycle will consist of 28 days.

Agent	Dose	Route	Administration Days	Frequency
Vemurafenib	960 mg	P.O.	Days 1-28	Twice daily for 28 days
Cobimetinib	60 mg	P.O.	Days 1-21	once daily for 21 days, followed by 7 days off

For both arms, a cycle will be 28 days. Patients will be treated with vemurafenib 960mg po twice daily for 28 days, and cobimetinib 60mg po once daily for 21 days, followed by 7 days off. Dose modifications will be instituted for toxicity as per [Section 8.0](#). Contrast- MRI (or CT, see [Section 5.0](#)) will be performed every 8 weeks as outlined in [Section 5.0](#). See [Section 11.0](#) for response criteria.

If a dose of vemurafenib is missed, it can be taken up to 4 hours prior to the next scheduled dose. If a dose of cobimetinib is missed (i.e. 6 hours or more late), do not make up that dose; resume dosing with the next scheduled dose.

If cobimetinib meets criteria to be discontinued due to protocol dose modifications and vemurafenib does not, cobimetinib may be discontinued and patient may continue on single agent vemurafenib therapy.

If vemurafenib meets criteria to be discontinued due to protocol dose modifications and cobimetinib does not, vemurafenib may be discontinued and patient may continue on single agent cobimetinib therapy.

See complete dose modifications in [Section 8.0](#).

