#### 8.1.12 QT prolongation: Chronic concomitant treatment with drugs that are known to prolong the QT interval/are associated with Torsades should be avoided, as vemurafenib can cause QT prolongation and arrhythmia. See [REDACTED] (registration required but is free).

- 8.1.13 Radiation recall:** Vemurafenib has been reported to cause radiation recall. For patients who develop CNS toxicity and were previously irradiated for craniopharyngioma, consider performing MRI brain to evaluate.
- 8.1.14 Malignancy:** Both vemurafenib and cobimetinib are associated with skin malignancies. Patients should report any new or suspicious skin lesions promptly, and have skin exams per [Section 5.0](#). In addition, vemurafenib is associated with RAS-related malignancies, and any suspicious symptoms should undergo prompt workup. In addition, vemurafenib is associated with the formation of colon polyps, and patients should follow national guidelines for colon screening.
- 8.1.15 Rash:** Both agents are associated with rash and cobimetinib is associated with photosensitivity. Patients should avoid sun exposure and practice good skin care. Consider dermatology consult as needed in the setting of rash.
- 8.1.16 Ocular toxicity:** Vemurafenib is known to cause uveitis, and cobimetinib is known to cause retinopathy. In addition, due to the location of the tumor, patients with craniopharyngioma are known to have visual field defects. Regular eye exams should be performed as per [Section 5.0](#), and patients should report any visual changes promptly. Consider treatment with steroids for uveitis. Serous retinopathy may be treated with topical corticosteroid eye drops.
- 8.1.17 Bleeding:** Cobimetinib leads to an increased bleeding risk. Hemorrhage, including major hemorrhages, defined as symptomatic bleeding in a critical area or organ, can occur with cobimetinib. In clinical studies with cobimetinib, events of cerebral hemorrhage, GI tract hemorrhage, reproductive tract hemorrhage, and hematuria have been reported. Patients on anticoagulation should undergo increased frequency of monitoring while on treatment.
- 8.1.18 Pneumonitis:** Cobimetinib has been associated with pneumonitis. In the setting of suspected pneumonitis, consider CT scan, PFTs, pulmonary consult, and bronchoscopy, and consider treatment with steroids or referral to pulmonary and infectious disease specialists.

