## 8.2 Dose modifications

- If multiple adverse events are seen, administer dose based on greatest modification required for any single adverse event observed.
- Modifications apply to treatment given in the preceding cycle and are based on adverse events observed since the prior dose.
- If study agent is held for >28 days, study agent will be discontinued.
- Dose modifications can be communicated to patients taking oral agents at home at any point in the cycle (i.e. if there is Grade III diarrhea at home).
- If cobimetinib meets criteria to be discontinued due to protocol dose modifications and vemurafenib does not, cobimetinib may be discontinued and patient may continue on single agent vemurafenib therapy.
- If vemurafenib meets criteria to be discontinued due to protocol dose modifications and cobimetinib does not, vemurafenib may be discontinued and patient may continue on single agent cobimetinib therapy.
- Descriptors below utilize CTCAE version 4.0. See Sections [9.1](#), [9.2](#) and [9.3](#) for routine AE reporting requirements. Expedited reporting via CTEP-AERS may be required for some adverse events (See [Section 9.3](#)). CTCAE version 5.0 must be used for serious adverse event reporting through CTEP-AERS.
- Please see IB for vemurafenib and cobimetinib or contact study chair for additional guidance.

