#### 8.2.2.6 Investigations:

- **Prior to initiation of treatment (i.e., after registration but prior to C1D1), for QTc  $> 500$  msec**, treatment not recommended. Consult with study chair prior to initiating treatment with vemurafenib and cobimetinib.
- For **grade 3 QTc interval prolonged**, delay vemurafenib until grade  $\leq 2$  then restart at 1 dose level decreased. Electrolytes (K, Mg, and Ca) should be monitored and any electrolyte abnormalities should be corrected prior to reinstitution of therapy.
- For **third occurrence of grade 3 QTc interval prolonged**, discontinue vemurafenib and cobimetinib.
- For **grade 4 QTc interval prolonged**, discontinue vemurafenib and cobimetinib.

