#### 8.2.2.7 Eye toxicity

- For **grade 2 uveitis**, delay vemurafenib until grade  $\leq 1$ , then resume at 1 dose level decreased.

- For **grade 3 or 4 uveitis**, discontinue vemurafenib and cobimetinib.
- For **grade 2 eye retinopathy**, delay cobimetinib until grade  $\leq 1$ , then resume at 1 dose level decreased.
- For **grade 3 or 4 retinopathy**, discontinue cobimetinib.
- For **retinal vascular disorder- retinal vein occlusion grade  $\geq 2$** , discontinue cobimetinib.

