## 12.0 END OF TREATMENT/INTERVENTION

### 12.1 Duration of treatment

**12.1.1 CR, PR, or SD:** Patients who are in CR, PR or SD will continue on therapy as outlined below:

- Cohort A: Patients can continue on therapy for a total of 4 cycles in cohort A, and then go on to receive radiation, surgery or both as outlined in [Section 7.1.1](#). In special circumstances, continuation of therapy with vemurafenib and cobimetinib may be granted, but only with approval from the radiation oncology chair (see [Section 7.1.1](#) for additional details). If continuation is approved, then therapy with cobimetinib and vemurafenib can continue until documented progression, unacceptable adverse events, or drug hold >28 days.
- Cohort B: Patients can continue therapy with cobimetinib and vemurafenib until documented progression, unacceptable adverse events, or drug hold >28 days (see [Section 7.1.2](#)). After treatment is completed or discontinued, patients will be followed per the study calendar in [Section 5.0](#).

**12.1.2 Disease progression:** Remove from protocol therapy any patient with disease progression. Document details, including tumor measurements, on data forms.

After disease progression, patients should be followed for survival per the study calendar ([Section 5.0](#)).

**12.1.3 Discontinuation of study agent:** If the patient discontinues protocol therapy due to reasons other than PD (i.e. for unacceptable adverse events, drug hold >28 days), prior to the completion of planned therapy as per [Section 7.0](#), patients should go on to clinical and survival follow up per the study calendar ([Section 5.0](#)). This includes:

- Patients who discontinue treatment before the end of 4 cycles of treatment to begin alternative therapy.
- Patients who discontinue continued treatment with vemurafenib and cobimetinib to begin alternative therapy (i.e. patients on Cohorts A or B who choose to continue therapy with vemurafenib and cobimetinib post the initial 4 cycles).

**12.1.4 Discontinuation of study agent in patients with expected AEs:** See [Section 8.2.4](#) for more information.

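### The closing eye exam is waived by reference to the last vemurafenib dose only, so a patient whose vemurafenib stops before cobimetinib can finish with no required retinal exam near the last cobimetinib dose

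*Combined protocol and SAP*

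**What the plan says.** Footnote A requires a retinal exam, slit-lamp exam and visual fields before registration, every 2 months (± 1 month) for the first year, every 6 months (± 2 months) after that while on protocol treatment, and once more within 28 days after treatment is completed. The last of these applies "ONLY if an eye exam has NOT been performed within 28 days prior to last dose of vemurafenib". The 4-week post-treatment visit in footnote ** lists no eye exam, so footnote A is the only closing requirement.

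On which drug carries the retinal risk, Section 8.1.16 states: "Vemurafenib is known to cause uveitis, and cobimetinib is known to cause retinopathy". Section 8.2.2.7 modifies cobimetinib alone for "grade 2 eye retinopathy", for higher grades of retinopathy and for retinal vein occlusion.

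On stopping one drug without the other, Section 7.1 says that, if only vemurafenib meets the criteria for discontinuation, "vemurafenib may be discontinued and patient may continue on single agent cobimetinib therapy". Section 8.2 repeats this and adds: "If study agent is held for >28 days, study agent will be discontinued".

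Two places point the other way. The schema reads "Discontinue vemurafenib + cobimetinib at progression, unacceptable adverse event, or drug hold" of more than 28 days. Section 12.1.1 lets patients continue on the two drugs "until documented progression, unacceptable adverse events, or drug hold >28 days".

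**The concern.** The waiver exists so that a recent exam can stand in for the closing one. It does so only if the exam was recent relative to the end of exposure to the drug being watched. If cobimetinib outlasts vemurafenib, an exam can be recent for vemurafenib and old for cobimetinib, and the rule still waives the closing exam. No eye exam is scheduled once protocol treatment has ended.

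At stake is a silent retinal finding in a patient still taking cobimetinib. Retinopathy, retinal detachment and retinal vascular disorder are adverse events of special interest at any grade (Section 9.3.2). Section 1.6.3 reports retinal detachment among the higher-grade events in the phase III melanoma trial at 2.4% with the combination and 0% with vemurafenib plus placebo. The visual-field report for that time point, used descriptively for exploratory objective 2.3.1, would also be missing.

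Elsewhere the calendar does take account of cobimetinib: footnote ** defines the end of treatment by both drugs, and footnote C ties the Echo/MUGA to time on cobimetinib.

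**Working it through.** The plan states no figure on this point, so the check is a reading of the rules plus day counts.

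**Which events separate the two drugs.**
- Holds written for vemurafenib alone are grade 3 acute kidney injury (8.2.2.3), grade 3 maculopapular rash (8.2.2.4), grade 2 ventricular arrhythmia (8.2.2.5), grade 3 QTc prolongation (8.2.2.6, "delay vemurafenib until grade" 2 or lower) and grade 2 uveitis (8.2.2.7). Uveitis would bring some eye follow-up of its own.
- Section 8.2.2.15 adds any other related grade 3 toxicity for which vemurafenib is the only responsible drug.
- Grade 3 hematuria is left out. The cobimetinib risk list counts it as hemorrhage, for which Section 8.2.2.12 also holds cobimetinib.
- The toxicity-specific rules that discontinue vemurafenib also stop cobimetinib. Vemurafenib alone is therefore discontinued only through the rule on holds of more than 28 days.

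**Dosing days.** Cycles are 28 days (7.1). Over four cycles vemurafenib runs to day 4 × 28 = 112. Cobimetinib is taken on days 1–21, 29–49, 57–77 and 85–105, which is 84 days. With no hold, vemurafenib is the later drug by 112 − 105 = 7 days.

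**Example 1: late hold, not more than 28 days, treatment ending at cycle 4.** Exam day 62, last vemurafenib day 88, hold still running at day 112.
- Waiver test: 88 − 62 = 26 ≤ 28, so the closing exam is waived.
- Hold length: 112 − 88 = 24 days, so the 28-day rules in the schema and Sections 8.2 and 12.1.1 are not triggered.
- Gap from exam to last cobimetinib: 105 − 62 = 43 days.
- Cobimetinib days after the exam: 15 (days 63–77) + 21 (days 85–105) = 36, and 36/84 = 43%.

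More generally, let the last vemurafenib dose fall on day L, from 85 to 104. The closing exam is waived with a gap above 28 days if the exam fell between day L − 28 and day 76. That is 76 − (L − 28) + 1 = 105 − L qualifying days, from 20 down to 1. The gaps run from 105 − 76 = 29 to 105 − 57 = 48 days.

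**Example 2: hold of more than 28 days.** Exam day 45, last vemurafenib day 50, cobimetinib continued alone to day 105.
- Waiver test: 50 − 45 = 5 ≤ 28, so the closing exam is waived.
- The hold passes 28 days on day 50 + 29 = 79.
- Gap: 105 − 45 = 60 days.
- Cobimetinib days after the exam: 4 + 21 + 21 = 46, and 46/84 = 55%.

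**Would the periodic schedule force another exam in time?** Not necessarily. The second on-treatment exam is due at 4 ± 1 months. Counted from the start of treatment, that window closes at about 5 × 30.4 = 152 days. Counted from a baseline exam as much as 28 + 10 = 38 days before day 1, it still closes no earlier than day 153 − 38 = 115, after day 112.

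**The case against.** The strongest reply is that vemurafenib is a sensible anchor. It is the later drug on the planned course, and the explicit toxicity rules that discontinue it take cobimetinib with it. This stands, and it is why few patients are exposed. It does not cover a vemurafenib hold still running when treatment ends.

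A second reply is that the schema and Section 12.1.1 end therapy with both drugs after a hold of more than 28 days. A reader might infer from Section 7.1 that the 60-day gap is plainly allowed. The documents do not settle that: Example 2 holds only if Sections 7.1 and 8.2 prevail. Example 1 does not depend on the answer. It does assume that treatment ends at cycle 4. A patient who continues and resumes vemurafenib moves the last dose, and the gap usually disappears.

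Third, footnote A accepts up to about 3 months (91 days) between exams during treatment, and the worked gaps are below the nominal 2-month interval. That is fair, and it limits the harm. But the 28-day tolerance is the one the footnote sets for its closing exam, after which no further exam is scheduled.

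A reader might also infer that only cobimetinib carries retinal risk, or that ocular monitoring lapses. Neither is supported. The nursing guidelines in Section 10.1 name retinitis and retinal vein occlusion under vemurafenib. Periodic eye exams continue on treatment, blurred vision is solicited each cycle, visual symptoms must be reported, and adverse events are assessed 4 weeks after treatment.

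**Conclusion.** The point holds as a minor gap in ocular safety monitoring. As written, footnote A can waive the closing exam for a patient with no required retinal exam within 28 days of the last cobimetinib dose. The gap is 43 days in the late-hold example, with a range of 29 to 48 days for that pattern. It can be longer, for example 60 days, after a hold of more than 28 days if cobimetinib alone is allowed to continue.

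This needs two things together: vemurafenib held or stopped alone while cobimetinib goes on, and an eye exam that happens to fall inside the 28-day window before the last vemurafenib dose. A reader might want a patient count. The documents give no rate for such holds, so none is claimed beyond the judgment that few patients, possibly none, would be affected. What could be missed is mainly a silent finding, since symptomatic events have other routes to detection. No efficacy endpoint, interim rule or final decision rule is affected.

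**What to change.** In footnote A, change the waiver so that it applies when an eye exam was done within 28 days before the last dose of vemurafenib or cobimetinib, whichever is later.

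With the last cobimetinib dose on day 105, and vemurafenib stopped earlier, an exam would then have to fall on days 77 to 105 to waive the closing one. The exams on days 62 and 45 would not qualify, so both example patients would have a closing exam. Patients on the planned course see no change, because vemurafenib is already their later drug.

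The cost is one phrase in one footnote and, in a very small number of patients, an eye exam that would otherwise have been waived. No new procedure is added.

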### Pre-Study Testing Intervals

- To be completed  $\leq 28$  DAYS before registration:
  - All laboratory studies, history and physical, eye exam
  - Any scan which is utilized for tumor measurement per protocol.
- To be completed  $\leq 60$  DAYS before registration: Any baseline exams used for screening that are not utilized for tumor measurement.

	Prior to Registration*	Day 1 of each cycle (cycle is 28 days)*	Weekly on treatment	Every 2 cycles	Monthly on treatment	Post treatment followup**	Clinical & survival follow- up ***
Tests & Observations							
History and physical, weight, PS	X(1)	X(1)				X(1)	X(1)
Height	X						
Pulse, Blood Pressure	X	X					X
Registration Fatigue/Uniscale Assessment	X(2)						
Adverse Event Assessment	X(3)	X(3)				X(3)	X(3)
EKG		B					
Echo or MUGA		C					
O2 Saturation		X(8)					
Eye exam	A	A				A	
Skin Exam		D					D
Patient Medication Diary		X(9)					
Laboratory Studies							
Complete Blood Count, Differential, Platelets	X	X					
Electrolytes, Creatinine (BMP)			X (10)				
Endocrine evaluation (with labs as necessary per endocrine evaluation)					X		
Chemistry	X(4)	X(4)				X(4)	
Serum or Urine HCG	X(5)						
Staging							
Central review for eligibility (pathology/BRAF)	X(6)						
MRI/CT Brain	X (7)			E(7)		E(7)	E(7)

Correlative studies: For patients who consent to participate in A071601-ST1				
Tissue block or slides				Archival tissue at baseline, recurrence and progression for banking and correlative science, see Section 6.2 .
Whole blood samples				Whole blood at prior to treatment, Day 1 of Cycle 3 (+/- 3 days), end of treatment, recurrence and progression, see Section 6.2 .

- \* Labs completed prior to registration may be used for day 1 of cycle 1 tests if obtained  $\leq 14$  days prior to treatment. For subsequent cycles, labs, tests and observations may be obtained +/- 3 days from scheduled day of assessment. Radiographic windows are +/- 7 days from scheduled day of assessment (except prior to registration). A new cycle is defined by day 1 on which the patient starts drug for that cycle.
- \*\* Physical examination, adverse event assessment, medication diary, and chemistry are required 4 weeks (+/- 7 days) after the end of treatment. End of treatment is considered 4-5 cycles of treatment, or end of treatment with vemurafenib + cobimetinib.

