- \*\*\* Patients who progress or who do not progress within 2 years from registration, will be followed for survival every 6 months, for a maximum of 5 years from registration (step 1). Patients discontinuing for reasons other than progressive disease will be followed for progression every 16 weeks (+/- 4 weeks) until they have reached 2 years post-registration or until documented progression (whichever comes first), then followed for survival every 6 months, for a maximum of 5 years from registration (Step 1). See also [Section 12.0](#).
- 1 History & physical should include neurologic exam and assessment of endocrine therapy (including dosage and type the patient is receiving).
- 2 To be completed after pre-registration and  $\leq 21$  days prior to treatment, see [Appendix I](#).
- 3 Solicited AEs are to be collected starting at baseline. Routine AEs are to be collected starting after registration. See [Sections 9.1](#) and [9.2](#). See also AEs of special interest in [Section 9.3](#). See [Section 9.4](#) for expedited reporting of SAEs.
- 4 Albumin, alkaline phosphatase, total bilirubin, bicarbonate, BUN, calcium, chloride, creatinine, glucose, potassium, total protein, SGOT[AST], SGPT[ALT], sodium and CPK. Glucose must be fasting (i.e., 8 hours or more fast).
- 5 For women of childbearing potential. Must be done  $\leq 7$  days prior to registration and  $\leq 7$  days prior to initiation of vemurafenib and cobimetinib
- 6 See [Sections 4.3](#), [4.4](#) and [6.2](#) for central review submission.
- 7 Scans can include either: 1) MRI Brain or 2) CT Brain. CT should ONLY be used for patients unable to undergo MR imaging because of non-compatible device or life-threatening gadolinium allergy. Also see [Section 11.0](#). Supporting documentation is to be submitted, per [Section 6.1.1](#). **All MRIs must be performed per [Appendix II](#) and submitted to IROC Ohio. Response assessment should include assessment of all sites of disease.** Baseline scan should be submitted to IROC within 14 days after patient registration per [Section 6.3](#). Any images required per footnote E or that are part of clinical care should be submitted to IROC Ohio within 14 days after acquisition per [Section 6.3](#).
- 8 Oxygen saturation should be assessed at rest and after 1 minute walk. Dose modifications for hypoxia should be followed per [Section 8.2.2.15](#).

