## 7.0 TREATMENT PLAN/INTERVENTION

Protocol treatment is to begin  $\leq 10$  days of registration. **EKG, Echo (or MUGA), O2 Saturation, and skin exam must be performed prior to initiation of treatment for safety as required in Section 5.0. See Dose Modifications in Section 8.2 prior to initiating treatment.** For questions regarding treatment, please see the study contacts page.

**Prior to initiating treatment, physicians must discuss caffeine limitation while on this study with the patient. See Section 8.1.11 for more information.**

It is acceptable for individual chemotherapy doses to be delivered  $\leq$  a 24-hour (business day) window before and after the protocol-defined date for Day 1 of a new cycle. For example, if the treatment due date is a Friday, the window for treatment includes the preceding Thursday through the following Monday. In addition, patients are permitted to have a new cycle of chemotherapy delayed up to 7 days for major life events (e.g., serious illness in a family member, major holiday, vacation that cannot be rescheduled) without this being considered a protocol violation. Documentation to justify this delay should be provided.

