#### 7.1.1 Cohort A

For Cohort A, patients should receive treatment for up to 4 cycles with vemurafenib + cobimetinib (unless progression, unacceptable toxicity, or patient withdrawal from study occurs). See [Section 12.0](#) for additional information. After 4 cycles of vemurafenib and cobimetinib, surgery or radiation for definitive therapy should be performed. Continuation of vemurafenib and cobimetinib beyond 4 cycles in cohort A will require approval from the radiation oncology chair and study chair. If patient stays on study for longer than 4 cycles, visits and labs at the beginning of every cycle are still required with scans every 2 cycles, as per the study calendar.

- **For patients that achieve CR**, they will undergo definitive radiation.
- **For patients with any response that is not CR or better**, the decision of therapy between surgery, or radiation, or both, is at the discretion of the treating physician.

**For patients who go on to receive radiation**, the pre-treatment scan would be used as a guide for radiation planning. See [Section 7.2](#) for radiation guidelines. Vemurafenib and cobimetinib need to be stopped at least two weeks prior to initiation of radiation therapy. For purposes of radiation planning, if duration of BRAF/MEK inhibitor treatment needs to be extended this will be allowed, for a maximum length of 4 additional weeks (i.e., 5 cycles maximum).

**In special cases**, if radiation or surgery are not recommended for the patient because of potential risks, then the patient may continue on cobimetinib and vemurafenib past 4 cycles, until disease progression or unacceptable adverse events. **However, continuation of treatment can only be granted with approval from the radiation oncologist and study chair.** A request, with accompanying rationale, must be sent to the radiation oncologist and protocol coordinator. Approval must be obtained via email prior to Cycle 5 drug shipment. The email containing the approval must also be submitted via Rave as supporting documentation.

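### A patient on 4 or 5 cycles can finish treatment with no required skin exam after baseline, because the first repeat is overdue only after about month 9

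*Combined protocol and SAP*

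**What the plan says.** Footnote D to the study calendar (Section 5.0) requires a skin exam before treatment, "then every 6 months (+/- 3 months) while on protocol treatment, then at discretion of treating physician once off protocol treatment". It also lists the findings to look for: "Skin exam should look for: rash, pruritis, dry skin, keratoacanthoma, squamous cell carcinoma, Hyperkeratosis, hand-foot syndrome".

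Treatment is short for many patients. Section 7.1.1 says "For Cohort A, patients should receive treatment for up to 4 cycles with vemurafenib + cobimetinib", with a fifth cycle allowed for radiation planning and anything longer only by special approval. Section 7.1.2 gives Cohort B 4 cycles, after which the treating physician may stop or continue the drugs.

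Section 7.0 groups the skin exam with three other tests: "EKG, Echo (or MUGA), O2 Saturation, and skin exam must be performed prior to initiation of treatment for safety". The calendar repeats the other three early. Oxygen saturation is marked for Day 1 of each cycle. The EKG is "then performed every 28 days (+/- 7 days) for 3 months". For cardiac function, "Echo or MUGA should be performed prior to treatment, after 1 month (+/- 5 days) of treatment", then every 3 months with a 1-month window.

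After treatment, "Physical examination, adverse event assessment, medication diary, and chemistry are required 4 weeks (+/- 7 days) after the end of treatment". The skin row is blank in that column. It carries a D under clinical and survival follow-up, where footnote D itself makes the exam discretionary. Section 8.1.14 refers the reader back to Section 5.0 for skin exams and adds none.

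**The concern.** The skin exam is the calendar's specific screen for skin malignancy, and Section 9.3.2 makes skin cancers of any grade events of special interest. A baseline exam cannot find a lesion that arises on drug. The first repeat falls so late that a patient treated exactly as Cohort A intends reaches the end of treatment before it is due, and from then on it is optional.

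For such a patient, finding a skin cancer after drug exposure can depend on general physical examinations and self-report. The calendar's note on the physical reads "History & physical should include neurologic exam and assessment of endocrine therapy"; it does not mention skin. At stake are the safety of individual patients and the completeness of the descriptive toxicity summary under objective 2.2.2. Section 1.6.1 reports cutaneous squamous cell carcinoma or keratoacanthoma in 19.2% to 25.8% of patients in three vemurafenib studies. That shows the risk is relevant, but it gives no rate for a 4-cycle course in this population.

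**Working it through.** The plan states no derived figure here, so there is none to reproduce. The check is calendar arithmetic, with 1 month = 30.44 days and 1 cycle = 28 days (Section 7.1).

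**When the repeat exam falls, counted from Cycle 1 Day 1 (footnote D)**
- Window opens: 3 × 30.44 = day 91, in cycle 4.
- Nominally due: 6 × 30.44 = day 183, in cycle 7.
- Overdue after: 9 × 30.44 = day 274; 274 / 28 = 9.8, so in cycle 10.

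**When treatment ends (Sections 7.1.1 and 7.1.2)**
- 4 cycles: 4 × 28 = day 112. Overdue date minus end of treatment: 274 − 112 = 162 days.
- 5 cycles: 5 × 28 = day 140. Overdue date minus end of treatment: 274 − 140 = 134 days.
- The nominal date also comes after treatment, by 183 − 112 = 71 days or 183 − 140 = 43 days. On this count, narrowing the window would not close the gap.

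**Sensitivity to the starting point.** Footnote D does not say where the interval starts. Suppose it runs from a baseline exam 70 days before first dose. This is an assumption: 60 days before registration, plus the 10 days that Section 7.0 allows to start treatment. The exam is then nominally due about day 113 (183 − 70) and overdue only after day 204 (274 − 70). That is still 204 − 140 = 64 days after a 5-cycle course. Five cycles with one 28-day hold end at day 168 (140 + 28), also before day 204.

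**Minimum repeats that must be done by day 112, for the four tests named in Section 7.0**

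| Test | Repeats that fall due | Minimum by day 112 |
|---|---|---|
| Oxygen saturation | Day 1 of cycles 2, 3 and 4 | 3 |
| EKG | Days 29, 57, 85 (latest 36, 64, 92) | 3 |
| Echo or MUGA | About 1 month (latest about day 35); the next is not overdue before 4 × 30.44 = day 122 | 1 |
| Skin exam | None | 0 |

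**Overlap with solicited adverse events (Section 9.1).** Of footnote D's seven target findings, only rash is on the solicited list (1 of 7). Keratoacanthoma and squamous cell carcinoma are not.

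**Patients concerned (Section 13.3.1).** Cohort A has 16 evaluable patients, or 16 + 2 = 18 with the allowance for ineligible patients and cancellations, less any approved to continue. To these are added Cohort B patients who stop after 4 cycles, whose number the plan does not give.

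**The case against.** The strongest reply is that this is a deliberate choice. Footnote D states a baseline, an interval, a window and a post-treatment rule, and nothing else in the protocol calls for an exam that the calendar fails to deliver. That is right: the point is a gap in the design, not a contradiction.

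The reply continues that other cover exists:
- History, physical examination and adverse event assessment take place each cycle, at the 4-week visit and in clinical follow-up.
- The calendar's adverse event note refers to Section 9.3, which includes skin cancers.
- Section 9.4.2 sends new malignancies, including non-melanoma skin cancers, for expedited reporting.
- Section 8.1.15 suggests a dermatology consult when needed for rash, and Section 10.1 has patients told to report new lesions.
- Section 5.0 leaves clinical monitoring to institutional guidelines and physician judgment.
- A site may do a compliant repeat from day 91, inside cycle 4.

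All of this narrows the gap. None of it is a required skin exam: reporting rules act once a lesion has been found, and the rest is general or discretionary.

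The comparison with the other three tests is also open to challenge. Those tests feed dose-modification rules, whereas Section 8.2.2.13 requires no cobimetinib change for a new malignancy. Different intervals can therefore be justified, and the table shows the gap without explaining it. Finally, 16 or 18 is an upper bound on Cohort A patients for whom a repeat is not compulsory. It is not a count of patients who would go unexamined.

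**Conclusion.** The concern holds, as a minor point of design. A Cohort A patient on plan, or a Cohort B patient who stops after 4 cycles, need have no dedicated skin exam after baseline, and no deviation arises. This is true whether the interval is counted from first dose or, on the stated assumption, from an exam 70 days earlier. It does not apply to patients who continue long enough to reach the required repeat; for them the schedule works.

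The number of lesions that could be missed cannot be computed from the documents, and none is claimed. The response endpoint, the two-stage design and its error rates are unaffected.

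**What to change.** Add one sentence to footnote D: any patient who stops drug without a post-baseline skin exam has one at the last on-treatment visit or no later than the 4-week post-treatment visit, with dermatology preferred but not required. Enter D for the skin row in the post-treatment follow-up column. Footnote A already uses a similar conditional end-of-treatment rule for the eye exam.

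The exam fits visits that already exist:
- After 4 cycles: day 85, or 112 + 28 = day 140 (133 to 147).
- After 5 cycles: day 113, or 140 + 28 = day 168 (161 to 175).
- After stopping at 1 cycle: 28 + 28 = day 56 (49 to 63).

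An exam at day 85 leaves the last four weeks of a 4-cycle course unexamined, so the post-treatment visit gives fuller cover. Doing the exam before radiation is convenient where feasible, but nothing here shows it to be necessary.

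The required minimum rises from 0 to 1 post-baseline exam per patient. The cost is one sentence, one calendar entry and at most one short exam at a visit that already includes a physical, or a referral where the site chooses dermatology. Patients already examined on treatment need nothing more, and findings go on the existing adverse event forms.
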